18.4 Investigator's Statement

This document, signed and dated by the Principal Investigator, describes the Investigator's obligations. The standard text is appended to the protocol ([Appendix 3](#)).

18.5 Monitoring Procedures

18.5.1 Study Monitoring

A CRO will be selected by the Sponsor to oversee the conduct of the trial. An appropriate representative of the CRO (Study Monitor) will maintain contact with the Investigator and will visit the study site for the purpose of discussing and/or retrieving data. An initiation (pre-study) visit will be made by the Study Monitor to discuss with the Investigator the protocol and the obligations of both the Sponsor and the Investigator. The Investigator must allow the Study Monitor to perform periodic, interim monitoring visits. The purposes of these visits are:

- To verify that written Informed Consent was obtained prior to each subject's participation in the trial.
- To assess the progress of the study.
- To review the compliance with the study protocol.
- To determine whether all adverse events were appropriately reported.
- To determine whether the Investigator is maintaining the essential documents.
- To discuss any emergent problem.
- To check the Case Report Forms (CRFs) for legibility, accuracy and completeness.

Version 1.0, 09May2015; Version 2.1, 16Nov2015; Version 3.0 (Amend. 1), 01Feb2016; Version 3.1 (Amend. 2), 28Apr2016; Version 3.2 (Amend. 3), 25May2016; Version 4.0 (Amend. 4), 29Nov2016; Version 5.0 (Amend. 5, Site-specific), 20Sep2017; Version 6.0 (Amend. 6), 29Sep2017; Version 7.1 (Amend. 7.1), Final 13 March 2018, Version 8.0 (Amend. 8.0), Final 23 April 2018; Version 10.0 (Amend. 10), Final 16 April 2019; Version 11.0 (Amend. 11), Final 24 Jun 2020

- To validate the contents of the CRFs against source documents.
- To collect completed CRFs.
- To assess the status of drug storage, dispensing and retrieval.

The Investigator will make available the source documents for inspection. This information will be considered as confidential. *Violations of and deviations from the protocol must be notified to the Study Monitor as soon as possible.*

The Study Monitor will perform a closeout visit at the time when all CRFs have been retrieved and all queries have been answered.

18.5.2 Case Report Forms (CRFs)

Electronic Case Report Forms (eCRFs) will be provided for each subject. The study Monitor will review the forms at each site visit.

Case Report Forms must be completed for all subjects who sign Informed Consent, even if the subject fails to complete the study. No section of the CRFs is to be left blank without an appropriate explanation by the Investigator, since the lack of such explanation may necessitate discarding an otherwise usable observation.

If requested, copies of the CRFs are to be made available to the appropriate regulatory agencies.

18.5.3 Auditing/Inspecting

The Investigator will make all pertinent records available, including source documentation, for inspection by regulatory authorities and for auditing by the Sponsor. This information will be considered as confidential. Audits/Inspections may occur any time from start to after conclusion of the study. When an Investigator signs the protocol, he/she agrees to allow regulatory authorities and **EryDel** auditors to inspect his/her study records.

18.6 Archiving of Records

Copies of the protocol, subject identification codes, eCRFs, source data, Informed Consent Forms and other documents pertaining to the study conduct must be kept for the maximum period of time as required by the study center. This time period must be at least two years after the last approval of the marketing application of the study agent in an ICH region and until there are no pending or contemplated marketing applications in an ICH region, or at least two years have elapsed since the formal discontinuation of clinical development of the study agent.

No study document should be destroyed without prior written agreement between the Sponsor and the Investigator. Originals of all documentation and copies of outgoing correspondence concerning the study will be stored and retained by the Sponsor in a safe area in the Trial Master File for the lifetime of the product. In particular, the final report sent by the Investigator to the IRB/IEC must be retained by the Sponsor, or the subsequent owner, for five years beyond the lifetime of the study agent.

18.7 Final Clinical Study Report

The Final Clinical Study Report (CSR) will be written by the CRO, according to specifications to be defined by **EryDel**.

Version 1.0, 09May2015; Version 2.1, 16Nov2015; Version 3.0 (Amend. 1), 01Feb2016; Version 3.1 (Amend. 2), 28Apr2016; Version 3.2 (Amend. 3), 25May2016; Version 4.0 (Amend. 4), 29Nov2016; Version 5.0 (Amend. 5, Site-specific), 20Sep2017; Version 6.0 (Amend. 6), 29Sep2017; Version 7.1 (Amend. 7.1), Final 13 March 2018, Version 8.0 (Amend. 8.0), Final 23 April 2018; Version 10.0 (Amend. 10), Final 16 April 2019; Version 11.0 (Amend. 11), Final 24 Jun 2020

18.8 Study Documentation and Publication of Results

Study Documentation

All unpublished documentation (including the protocol, CRFs and Investigator's Brochure) given to the Investigator is strictly confidential. All recipients must agree not to disclose the information herein contained to any person not connected with the study without the prior written authorization of **EryDel S.p.A.** The submission of these documents to the IRB/IEC is expressly permitted. The involved parties agree that the results of this study will be used in their original form and/or in a global report for submission to governmental and regulatory authorities of any country.

All information communicated to the investigator(s) by **EryDel** is the exclusive property of **EryDel S.p.A.** The Principal Investigator will ensure this information shall be kept strictly confidential by him/her or any other person connected with the study and shall not be disclosed to any third party without the prior written consent of **EryDel**.

Publication of Results

Any formal presentation or publication of the data from this trial will be considered as a joint publication by the Investigator(s) and EryDel. Authorship will be determined by a Publication Committee consisting of the lead investigator(s) from the trial, representatives from EryDel, and an external consultant with expertise in the field. For multi-center studies, it is mandatory that the first publication is based on data from all centers, analyzed as stipulated in the protocol by a statistician designated by EryDel. Investigators participating in this study agree not to present or publish data gathered from a single center or sub-group of centers before the full initial publication, unless agreed to by all other investigators and EryDel. Authorship of any publication resulting from this trial will include members of each of the contributing centers and key contributors to the design and execution of the study, including EryDel personnel.

EryDel will form a study publication committee to coordinate and develop a publication policy and help in its implementation. The publication committee will be comprised of the Principal Investigators from each of the countries (to be determined by EryDel), based on their contributions to study conduct and their status in the field. The other members of the publication committee will include a representative of EryDel and an external consultant. Members of the publication committee cannot serve as first authors of more than one primary publication.

The authorship of the first multicenter paper will be comprised of members of the publication committee, Principal Investigators of the three sites with the highest numbers of valid patients, and EryDel representatives who have made significant contributions to the design, conduct and analysis of the results. The Principal Investigators of all contributing centers will be acknowledged in the publication. The Publication Committee will decide on the content, journal, and sequence of publications /presentations.

Any publication, abstract, or paper of any information or material relating to or arising out of the present clinical study shall be sent to EryDel for review at least sixty (60) days before presentation at any congress, or publication of the final form(s) by any journal. EryDel will inform the Investigator of any changes or deletions necessary to preserve EryDel's confidential and proprietary technical information. All rights and interests worldwide in any inventions, know-how or other intellectual or industrial property rights, which arise during the course and/or as a result of the present clinical study or which arise from the information or materials supplied under this Agreement, shall be assigned to, vest in and remain the property of EryDel S.p.A.

18.9 Financial Agreement

A financial agreement (separate from the protocol) will be made and signed by **EryDel S.p.A.** or their designee and by a representative of the Institution where the study will be conducted.

18.10 Termination of Study

In the event that the Investigator is unable to continue the study, another suitable sub-Investigator at the site will be designated to serve as the Investigator in the interim, until a new Investigator can be identified. This interim Investigator, if approved by the site IRB/IEC will carry out the responsibilities of the Investigator. Documentation testifying to this will be submitted to the Study Monitor within 10 days of the change. Within 6 months of the appointment of the interim Investigator, the new Principal Investigator must be identified and approved by both **EryDel S.p.A.** and the IRB/IEC for the study to continue at the site.

If the Sponsor and/or the Investigator should discover conditions arising during the study that indicate it should be terminated, an appropriate schedule for termination will be instituted. If the Investigator terminates the study, an explanatory letter will be provided to **EryDel**. Should the study be discontinued due to a decision by **EryDel**, the Investigator will be reimbursed for reasonable expenses incurred and for the subjects actually treated according to the study protocol.

18.10.1 Study Discontinuation by the Sponsor

The Sponsor may terminate the entire study, or the study at an individual site, at any time, for any of the following reasons:

- failure to enroll subjects;
- protocol violations or deviations;
- inaccurate or incomplete data;
- non GCP compliance;
- completion of enrolment;
- administrative reasons.

18.10.2 Study Discontinuation by the Investigator

The Investigator may terminate his/her participation in the study in consultation with the Sponsor due to the occurrence of significant adverse events and/or adverse drug reactions endangering the health of subjects, which make it ethically unacceptable to continue.

18.11 Insurance Policy

EryDel S.p.A., or its designee, will provide insurance coverage for damages emerging from the trial and involving the subjects treated with the test compound, provided that the Investigator(s) have adhered to the terms and provisions of the protocol. The principal Investigator will be supplied with all data concerning the insurance company and policy number for a maximum sum insurable.

18.12 Financial Disclosure

The Principal Investigator and sub-Investigators will provide the Sponsor with adequate and accurate financial information (PD35) to ensure that the Sponsor can make complete and accurate financial certification of disclosure statements to concerned regulatory authorities. It is the duty of the Investigator to promptly update previous information provided to the Sponsor if there are salient changes that occur during the course of the study, and for a period of one year following its completion (last patient last visit).

The study will be performed under a US IND; therefore, all Investigators/sub-Investigators, contractors, etc., are expected to comply with the obligations as specified in the CFR (21 CFR part 54) by the US FDA,

Version 1.0, 09May2015; Version 2.1, 16Nov2015; Version 3.0 (Amend. 1), 01Feb2016; Version 3.1 (Amend. 2), 28Apr2016; Version 3.2 (Amend. 3), 25May2016; Version 4.0 (Amend. 4), 29Nov2016; Version 5.0 (Amend. 5, Site-specific), 20Sep2017; Version 6.0 (Amend. 6), 29Sep2017; Version 7.1 (Amend. 7.1), Final 13 March 2018, Version 8.0 (Amend. 8.0), Final 23 April 2018; Version 10.0 (Amend. 10), Final 16 April 2019; Version 11.0 (Amend. 11), Final 24 Jun 2020

including requirements for full Financial Disclosure ([Guidance for Clinical Investigators, Industry and FDA Staff: Financial Disclosure by Clinical Investigators, February 2013](#)).

MCHC	Mean Corpuscular Hemoglobin Concentration
MITT	Modified Intention to Treat
OC	Observed Cases
pBAR	Probabilistic Baseline Randomization
PD	Pharmacodynamics
PK	Pharmacokinetics
PP	Per Protocol
QOL	Quality of Life
RBC	Red Blood Cell
RDO	Retrieved Dropout
RDW	Red Cell Distribution Width
SAP	Statistical Analysis Plan
SGOT	Serum Glutamic Oxaloacetic Transaminase
SGPT	Serum Glutamic Pyruvic Transaminase
SP	Safety Population
TEAE	Treatment Emergent Adverse Event
VABS	Vineland Adaptive Behaviors Scale
WBC	White Blood Cell

1. INTRODUCTION

The purpose of Study IEDAT-02-2015, A Multi-center, Randomized, Double-blind, Placebo-controlled Trial to Evaluate the Effects of Intra-Erythrocyte Dexamethasone Sodium Phosphate on Neurological Symptoms in Patients with Ataxia Telangiectasia, is to demonstrate the safety and efficacy of the EryDex System end product (EDS-EP) in subjects with ataxia telangiectasia (AT). The EDS is a combination product that is used to load dexamethasone sodium phosphate (DSP) into autologous erythrocytes, creating the EDS-EP, which is infused into the patient.

This Statistical Analysis Plan (SAP) describes the planned analysis and reporting for protocol IEDAT-02-2015 Version 11.0, Final, 24 June 2020.

The purpose of this SAP is to outline the planned analyses to support the completion of the Clinical Study Report (CSR) for study IEDAT-02-2015. The planned analyses identified in this SAP will be included in regulatory submissions and/or future manuscripts. Exploratory analyses not necessarily identified in this SAP may be performed to support the clinical development program. Any *post hoc* or unplanned analyses not identified in this SAP will be clearly identified as such in the CSR.

This document includes the analysis of the initial treatment period (Period 1) and the extension treatment period, which consists of Period 2 [Visit 9 (Month 6) to Visit 12 (Month 9)] and Period 3 which consists of [Visit 12 (Month 9) to V15 to Month 12].

Low dose is defined as an approximate dose range between 5-10 mg EDS-EP and high dose is defined as an approximate dose range between 14-22 mg EDS-EP. This document is referencing placebo, low dose, and high dose.

All subjects who complete 12 months of treatment in the trial, complete the study assessments (and Retrieved Dropouts who return for the final Visit 15 [“Month 12”] efficacy assessment), and provide informed consent will be eligible to continue treatment with EDS-EP in an open-label, extension study (IEDAT-03-2016).

1.1 Study Objectives

The proposed study was designed to assess the efficacy and safety of administration of two dose levels of EDS-EP, when compared with placebo, in subjects with AT.

Initial Treatment Period

Primary Efficacy Objective:

- To evaluate the effect of two dose ranges (~5-10 and ~14-22 mg DSP/infusion) of EryDex System end product (EDS-EP), compared to placebo, on central nervous system (CNS) symptoms measured by the Modified International Cooperative Ataxia Rating Scale (mICARS) in subjects with AT. The Full ICARS will also be evaluated.

Key Secondary Efficacy Objective:

- To evaluate the effect of EDS-EP, compared to placebo, in this population on the Clinical Global Impression of Change from baseline (CGI-C).

Safety Objective:

- To evaluate the safety and tolerability of EDS-EP, compared to placebo, in AT subjects, based on the occurrence of Treatment-Emergent Adverse Events (TEAEs), including

Serious Adverse Events and discontinuations due to adverse events, and changes in vital signs, laboratory parameters, ECGs and physical/neurological examination findings.

Other Secondary Efficacy Objectives:

- To evaluate the effect of EDS-EP, compared to placebo, in this population on the Clinical Global Impression of Severity (CGI-S; structured)
- To evaluate the effect of EDS-EP, compared to placebo, in this population, on adaptive behavior measured by the Vineland Adaptive Behavior Scales (VABS).

Tertiary Objectives:

- To evaluate the effect of EDS-EP on health-related Quality of Life (QoL) using the EQ-5D-5L scale;
- To assess the pharmacokinetic and pharmacodynamic relationships between dexamethasone administered through EDS-EP and safety, tolerability, and demographic variables;
- To evaluate the pharmacokinetic (PK) profile of dexamethasone administered through EDS-EP at two dose levels based on pooled data from all subjects in each treatment group. A determination of individual PK parameters will be performed for subjects with an adequate number of PK blood samples after the initial infusion.

Exploratory Objective:

- To collect data on the use of the Ataxia-Telangiectasia Neurological Examination Scale Toolkit (A-T NEST) concurrent with the ICARS, CGI-S (structured) and CGI-C, as well as its use in languages other than English, and to compare it with the data from the scales referenced to assess the psychometric properties of the A-T NEST.

All data collected on the A-T NEST from selected study centers on Day 2 and subsequent visits will be delivered to John Hopkins Statistical group for evaluation of the data, and performance of any analyses needed to determine/confirm the psychometric properties of the scale, and such analysis will be described in documentation apart from this statistical analysis plan.

Extension Treatment Period**Primary Objective:**

- To evaluate the efficacy of two dose ranges (~5-10 and ~14-22 mg DSP/infusion) of EDS-EP, compared to placebo, in treating CNS symptoms in AT subjects during long-term treatment, as measured by the Modified ICARS. The Full ICARS will also be evaluated.

Secondary Objectives:

- To evaluate the long-term safety and tolerability of EDS-EP in AT subjects;
- To compare the effects of the two dose ranges of EDS-EP on the clinician's global impression (CGI-C and CGI-S [structured]), adaptive behavior (VABS), and QoL (EQ-5D-5L scale).

1.2 Study Design

This is an international (North America, Europe, Africa, Asia, and Australia), multi-center, one year, randomized, double-blind, placebo-controlled, Phase III study, designed to assess the effect of two non-overlapping dose ranges of EDS-EP, administered by IV infusion once per month, on neurological symptoms of subjects with AT. All subjects who complete the assessments as designed over the initial treatment period of the trial will be eligible to continue in an additional double-blind, placebo-controlled extension designed to collect information on the long-term safety and efficacy of the trial treatments.

The protocol planned for 180 subjects to be enrolled, and those meeting all of the inclusion/exclusion criteria were randomized to receive one of the two dose ranges of EDS-EP or placebo (1:1:1 with the intent of randomizing 60 subjects per group) as follows:

- **Group 1, Low Dose, EDS-EP low dose range of ~5-10 mg DSP/infusion:** CCI
[REDACTED]
- **Group 2, High Dose, EDS-EP high dose range of ~14-22 mg DSP/infusion:** CCI
[REDACTED]
- **Group 3, Placebo EDS infusion:** CCI
[REDACTED]

Due to the impact of COVID-19, the company decided to complete enrollment with 175 patients.

A minimization procedure was employed to ensure that the proportions of male and female, and younger (6 to <10 years) and older (≥ 10 years) subjects are comparable across the three treatment groups. Every attempt was made to ensure the same balance was achieved across different regions. In the Initial Treatment Period, each subject will receive 6 infusions of EDS-EP (low or high dose) or placebo, given at monthly intervals. Similarly, subjects entering the Extension Treatment Period will continue on the randomized treatment and will receive 6 monthly infusions of EDS-EP or placebo.

Randomization/placebo switching will take place at 3 time points, as described in [Section 5.1.7](#).

1.3 Study Timepoints

Study visits, associated target days, and associated target visit windows are presented in Tables 1 and 2 for the initial treatment period and the extension treatment period, respectively. Per database specifications, most data are collected on visit specific CRFs and therefore the scheduled visit number is inherently assigned in such cases.

For all analysis populations (see Section 2 of this statistical analysis plan) except the Per Protocol Population, if data are recorded on a CRF with a scheduled visit, the data will be associated with the scheduled visit for analysis and listing purposes.

For the Per Protocol Population, data records will be associated with a visit for analysis and listing according to the target visit windows in Tables 1 and 2; note that each visit assignment will be made relative to the day of the immediately preceding dose. Subject exclusion from the Per

Protocol Population will depend upon the elapsed time between first dose and the “Month 6” visit, and also upon the number of doses missed prior to the “Month 6” visit (see [Section 2](#)).

Table 1. Study Timing: Initial Treatment Period

Visit	Target Day	Target Visit Window
Screening	-30 to -1	
Visit 1	Day 0/1	
Visit 2	2	
Visit 3	15	15±7 days
Visit 4	30	Not before 21 days after the prior infusion (Infusion 1), +10 days
Visit 5	60	Not before 21 days after the prior infusion (Infusion 2), +10 days
Visit 6	90	Not before 21 days after the prior infusion (Infusion 3), +10 days
Visit 7	120	Not before 21 days after the prior infusion (Infusion 4), +10 days
Visit 8	150	Not before 21 days after the prior infusion (Infusion 5), +10 days
Visit 9	180	Not before 21 days after the prior infusion (Infusion 6), +10 days

Note: As a result of the defined target visit window intervals in protocol Version 10, the maximum possible number of days per protocol in the initial treatment period is 228 days.

Table 2. Study Timing: Extension Treatment Period

Visit	Target Day	Target Visit Window
Visit 9a	180	Not before 21 days after the prior infusion (Infusion 6), +10 days
Visit 10	210	Not before 21 days after the prior infusion (Infusion 7), +10 days
Visit 11	240	Not before 21 days after the prior infusion (Infusion 8), +10 days
Visit 12	270	Not before 21 days after the prior infusion (Infusion 9), +10 days
Visit 13	300	Not before 21 days after the prior infusion (Infusion 10), +10 days

Table 2. Study Timing: Extension Treatment Period

Visit	Target Day	Target Visit Window
Visit 14	330	Not before 21 days after the prior infusion (Infusion 11), +10 days
Visit 15	360	Not before 21 days after the prior infusion (Infusion 12), +10 days
Visit 16	390	30 days after subject final assessment or at least 60 days after their last infusion, whichever is longer

The schedule of assessments for the initial treatment period and extension treatment period is in [Appendix I](#).

2. STUDY POPULATIONS

The following analysis sets will be used:

- Safety Population (SP): all subjects who received any amount of randomized treatment.
- Full Analysis Set (FAS) (also referred to as MITT – Modified Intent-to-Treat): All randomized subjects who received at least one dose of study medication and had at least one post-baseline efficacy assessment of the primary efficacy variable.
- Per Protocol Population (PP): all subjects enrolled into the study who fulfilled all Inclusion/Exclusion criteria, did not have any major protocol violations, and completed the Initial Treatment Period of the study as planned. Completing the initial treatment period of the study as planned will include subject completion of at least 5 doses of treatment (allowing ≤ 1 missed dose, see [Section 5.2.4](#)), including the Visit 8 dose and the ICARS and CGI-C assessments performed at Visit 9 (“Month 6”) within 228 days. Subjects who discontinue the investigational product prematurely due to AEs, without protocol violations, and return for their final evaluation, will still be part of the PP population. Additional per protocol populations, including patients who complete the initial treatment period within a duration greater than 228 days, may be identified and used for sensitivity analyses.

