
Analysis Populations
	
The following analysis sets will be used:
 
 1) Intention-to-treat population (ITT): All randomized patients. 2) Full Analysis Set (FAS) (Also referred to as MITT): All randomized patients who received at least one dose of study medication and had at least one post-baseline efficacy assessment of the primary efficacy variable. 3) Per Protocol Population (PP): All patients enrolled into the study who received at least one dose of randomized treatment, fulfilled all Inclusion/Exclusion criteria, did not have any major protocol violations, and

Clinical Study Protocol IEDAT-02-2015

EDS in Ataxia Telangiectasia Patients

Version 1.0, 09May2015; Version 2.1, 16Nov2015; Version 3.0 (Amend. 1), 01Feb2016; Version 3.1 (Amend. 2), 28Apr2016; Version 3.2 (Amend. 3), 25May2016; Version 4.0 (Amend. 4), 29Nov2016; Version 5.0 (Amend. 5, Site-specific), 20Sep2017; Version 6.0 (Amend. 6), 29Sep2017; Version 7.1 (Amend. 7.1), Final 13 March 2018, Version 8.0 (Amend. 8.0), Final 23 April 2018; Version 10.0 (Amend. 10), Final 16 April 2019; Version 11.0 (Amend. 11), Final 24 Jun 2020

	
completed the Initial Treatment Period of the study as planned (i.e. returned for a final evaluation).
 
4) Safety Population (SP): All patients who received at least one dose of randomized treatment.

--	---

Clinical Study Protocol IEDAT-02-2015

EDS in Ataxia Telangiectasia Patients

Version 1.0, 09May2015; Version 2.1, 16Nov2015; Version 3.0 (Amend. 1), 01Feb2016; Version 3.1 (Amend. 2), 28Apr2016; Version 3.2 (Amend. 3), 25May2016; Version 4.0 (Amend. 4), 29Nov2016; Version 5.0 (Amend. 5, Site-specific), 20Sep2017; Version 6.0 (Amend. 6), 29Sep2017; Version 7.1 (Amend. 7.1), Final 13 March 2018, Version 8.0 (Amend. 8.0), Final 23 April 2018; Version 10.0 (Amend. 10), Final 16 April 2019; Version 11.0 (Amend. 11), Final 24 Jun 2020

Schedule of Visits and Assessments: 6-Month Initial Treatment Period

Visit (V) (z)	Screening	V1		V2	V3	V4	V5	V6		V7	V8	V9
Study Day or Month (D/M) #	D -30 to -1	D0/1	D2	D15	M1	M2	M3	M4	M5	M6 (a,b)		
Procedure (§)		Pre(c)	Post(c)					Pre(c)	Post(c)			
Informed Consent Signature	X											
Medical History/Demographics	X											
Inclusion/Exclusion Criteria (v)	X	X										
EDS-EP Infusion (h)		1				2	3	4		5	6	
Culture-based sterility test (aa)			X			X	X		X	X	X	
Neurological Examination	X	X						X				X
Physical Examination	X	X	X			X	X	X	X	X	X	X

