16.2.2 Populations for Analysis

The following analysis sets will be used:

- 1) *Intention-to-treat population (ITT)*: All randomized patients.
- 2) *Full Analysis Set (FAS)* (Also referred to as MITT): All randomized patients who received at least one dose of study medication and had at least one post-baseline efficacy assessment of the primary efficacy variable.
- 3) *Per Protocol Population (PP)*: all patients enrolled into the study who received at least one dose of randomized treatment, fulfilled all Inclusion/Exclusion criteria, did not have any major protocol violations, and completed the Initial Treatment Period of the study as planned (ie, returned for a final evaluation). Patients who discontinue prematurely for reasons other than protocol violations, but return for their final evaluation, would still be part of the PP population, e.g. patients who discontinue due to AEs should be included.
- 4) *Safety Population (SP)*: all patients who received at least one dose of randomized treatment.

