5.3 Efficacy Analysis

All efficacy analyses will be performed on both the FAS and PP populations.

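### The SAP narrows the protocol's Per Protocol set so that an early stopper's membership depends on the recorded reason for stopping, and does not list this as a change

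*SAP*

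**What the plan says.** The protocol synopsis includes in PP patients without major violations who "completed the Initial Treatment Period of the study as planned (i.e. returned for a final evaluation"). Section 16.2.2 gives the same meaning and adds a rule for early stoppers: "Patients who discontinue prematurely for reasons other than protocol violations, but return for their final evaluation, would still be part of the PP population". It then illustrates the rule: "e.g. patients who discontinue due to AEs should be included". Neither place sets a dose count.

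SAP Section 2 gives completion a different meaning: "Completing the initial treatment period of the study as planned will include subject completion of at least 5 doses of treatment", "including the Visit 8 dose and the ICARS and CGI-C assessments performed at Visit 9", all within 228 days. SAP 1.3 repeats that exclusion depends on elapsed time and "also upon the number of doses missed prior to the “Month 6” visit". The only early stoppers released from this are those in the sentence "Subjects who discontinue the investigational product prematurely due to AEs, without protocol violations, and return for their final evaluation, will still be part" (the set meant is PP).

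SAP 5.3 sets the reach of the definition: "All efficacy analyses will be performed on both the FAS and PP populations".

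SAP 5.10, the section for departures from the protocol, lists two: the dropped analysis of observed cases plus retrieved dropouts (OC+RDO), and visit timing that ran past 12 months. The PP definition is not mentioned. To justify the first departure, 5.10 states that no retrieved dropout would be lost from any of the four analysis populations. SAP 5.1.9 names those four as ITT, FAS, Safety and PP.

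**The concern.** A dose floor is a reasonable thing to want in a PP set. This one is applied unevenly. A patient who stops after one infusion for an adverse event and returns is per protocol. A patient who receives five infusions, stops for another reason before Visit 8 and returns is not. Between two patients with the same exposure, the recorded reason for stopping decides who is in the set.

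Reason for stopping is a post-randomisation variable that may be related to arm and to course. Protocol 9.4 asks early stoppers to come back for the Month 6 evaluation, so these are observed outcomes, and the SAP leaves some of them out of PP.

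Two practical matters follow. The blinded data review meeting has to apply one PP definition and is given two. And a reader of the PP tables who relies on 5.10 would not learn that the set is narrower than the protocol's.

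**Working it through.** **Figure inside the SAP rule.** The 228-day limit follows from six intervals of at most 28 days plus a 10-day window (Protocol 11.2; SAP Table 1): 6 × (28 + 10) = 228. It reproduces.

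**PP status by stopping point.** Infusions 1 to 6 fall at Visits 1, 4, 5, 6, 7 and 8 (protocol flow chart). Take a patient without a major violation who stops early, misses no dose before stopping, and returns for the Visit 9 ICARS and CGI-C within 228 days.

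| Last infusion | Doses | Visit 8 dose | Protocol PP, any reason | SAP PP, AE | SAP PP, other reason |
|---|---|---|---|---|---|
| Visit 1 | 1 | no | in | in | out |
| Visit 4 | 2 | no | in | in | out |
| Visit 5 | 3 | no | in | in | out |
| Visit 6 | 4 | no | in | in | out |
| Visit 7 | 5 | no | in | in | out |

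The documents disagree at 5 of 5 points for the non-AE stopper and at none for the AE stopper. The fifth row shows that the Visit 8 condition does the work there: five doses meet the count, and the patient is still out.

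**Who is in the last column.** Every non-AE reason: for example consent withdrawal (a listed reason in Protocol 15.2), where the patient still returns, and COVID-19, which SAP 5.2.1 names among the reasons for PP exclusion.

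**Consistency with SAP 5.10.** A patient who stops after infusion 3 for a non-AE reason and returns at the scheduled efficacy visits is a retrieved dropout. Section 2 puts this patient outside PP; 5.10 says no such patient is outside any population. The 5.10 statement is true for non-violators under the protocol rule and false for non-AE stoppers under the SAP rule.

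**Possible size.** The documents give no rate of returning non-AE stoppers, so what follows is by assumption.

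- Number: in the Phase II AT study 4 of 22 stopped, 2 for AEs, 1 for a violation and 1 by consent withdrawal. Only the last could be classified differently, and only on return. With 175 / 3 = 58.3 per arm, 1/22 × 58.3 = 2.7 per arm, from a single patient and before any COVID-19 stoppers.
- Shift in one arm's PP mean: k × d / n, for k patients removed from n who are d points worse than the rest. With k = 3, n = 55 and d = 3 to 5 (all assumed): 3 × 3 / 55 = 0.16 and 3 × 5 / 55 = 0.27 mICARS points, or 5% to 9% of the 3.0-point planning difference.
- A harsher case: a fraction q removed from one arm and none from the other, with stopping correlated r with the change score. Shift = r × SD × φ(z₁₋q) / (1 − q). With r = 0.5, q = 0.05 and SD 5 this is 0.27; with q = 0.10 and SD 8 it is 0.78. Perfect tracking (r = 1) doubles these to 0.54 and 1.56.
- Direction: higher mICARS is worse. Taking poor outcomes out of placebo shrinks the PP benefit; taking them out of an active arm enlarges it.

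For scale, the standard error of a single-visit difference at SD 7 with 54 per arm is 7 × √(2/54) = 1.35.

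**The case against.** The strongest reply is that this is a wording mismatch in a supportive set. Trial success rests on the FAS, which keeps any of these patients who was dosed and has a post-baseline ICARS. PP exclusions are agreed and signed at a meeting held before unblinding (SAP 5.2.2) and tabulated by reason and treatment (SAP 5.2.1), so an imbalance would show. The SAP states its rule openly in Sections 1.3 and 2 and allows further PP sets for sensitivity. Minimum exposure is a normal purpose of a PP set, and the protocol rule would count a patient with one infusion as per protocol.

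Most of this stands, and it limits the point to PP. It does not explain why the exposure rule is waived for one reason and enforced for all others. Blinded review prevents case-by-case selection, but it does not remove a dependence written into the rule.

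A reader might go further and infer that the SAP removes lack-of-efficacy patients by outcome, mostly from placebo, and so manufactures support for the FAS result. The documents do not bear that out. No outcome enters the rule. Protocol 15.2 does not list lack of efficacy as a withdrawal reason. In the sponsor's controlled IBD study in Protocol Table 1, lack-of-efficacy stops were 19.0% on active and 16.7% on placebo, with no adverse dropouts; the Crohn's study in the same table leans towards placebo; the Phase II AT study had none. And if poor outcomes were removed from placebo, the PP effect would shrink.

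**Conclusion.** The point holds as a conflict between the two documents and as an uneven rule. The SAP excludes from PP every returning non-violator who stopped for a non-AE reason before the Visit 8 infusion, whom the protocol includes; it keeps AE stoppers at any dose count; it does not list the change in 5.10; and 5.10 makes a statement about retrieved dropouts that Section 2 contradicts. These conclusions rest on the texts alone.

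Size and direction are unknown. The illustrative shifts of 0.16 to 0.27 points, or 0.27 to 0.78 under the harsher case at r = 0.5, rest on assumed counts, differences and correlations and are not estimates. They are below one standard error of a single-visit difference at SD 7. The 10% planning allowance does not measure the affected group either, since patients lost to follow-up do not return and are outside PP under both documents.

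The success criterion is not affected. Every PP efficacy analysis is, which makes this worth correcting before the PP set is fixed.

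**What to change.** Before the blinded data review meeting:

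1. Use the protocol rule in SAP Section 2: a patient with no major violation who stops treatment for any other reason and has the Visit 9 ICARS and CGI-C stays in PP. Align SAP 1.3 with it.
2. If a dose-adherent set is wanted, define it as a separate sensitivity set, apply the 5-dose and Visit 8 conditions whatever the reason for stopping, and list it in 5.10.
3. Check the 5.10 statement about retrieved dropouts against the final definitions and correct it.

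Listing the present rule in 5.10 with a rationale would cure the non-disclosure, but membership would still depend on the reason for stopping.

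The cost is SAP wording only. The main PP set would have no dose floor and so be less adherent, and running both sets adds one set of tables.
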